All patient participants will follow the usual physiotherapy care pathway within RÖ and RJL and will therefore have access to other healthcare professions, resources and healthcare levels for additional consultation or management should any unexpected adverse event occur. There will be no restrictions placed on seeking other care during the trial period. Following completion of the study the patients will follow the usual management pathway.

Ethics

This study has been approved by the Swedish Ethical Review Authority (Etikprövningsmyndigheten). Diary number (Dnr): 2023-05968-01 (25/10/2023). An amendment to the initial ethical application outlining the concluding qualitative phase of the RCT and follow-up questionnaire for participating physiotherapists was submitted to the Swedish Ethical Review Authority on the July 1st, 2024. This amendment was approved on the July 21st, 2024 (Dnr: 2024-04524-02).

Contact details:

Swedish Ethical Review Authority, [name].
Email: [contact]. [contact]

Consent

Participant recruitment: All potentially eligible patient participants will receive standardised verbal or text information about the study from the triaging physiotherapist and be asked for consent to share their contact details with the study coordinators. If preliminary consent is obtained, then standardised information will be sent to potential participants via a SMS-link to a Webropol questionnaire. This information contains contact details to the study coordinators and those responsible for the study. Patients who provide consent will gain immediate access to the baseline questionnaire.

Physiotherapist recruitment: All participating physiotherapists will provide definitive consent after receiving verbal information at workplace meetings and further written information in-line with the patient participant recruitment. Consent will be collected via online Webropol questionnaires. Participation in the qualitative phase: all physiotherapists that have consented to the RCT and conducted at least one PainSMART-consultation prior to the start of the qualitative phase will be invited to continue their participation. The eligible physiotherapists will be informed about the qualitative phase by their local PainSMART champion and asked for verbal consent.

Confidentiality

The personal details of eligible patients will be shared with the study coordinators via the secure electronic journal system used within RÖ and RJL. All participants (patients and physiotherapists) will receive a unique code-key number to enable pseudonymisation of data and secure data storage within the Webropol system (RÖ) and SPPS program (Linköping's University). The code-keys for the patient and physiotherapist participants will be stored separately from the secure Webropol (RÖ) server and Linköping's University data analysis programs. The physiotherapists' evaluations of the initial consultations will be stored pseudonymised by the use of a code-key. All results will be published at group level. All audio recordings will be deleted from Dictaphones immediately after being uploaded to the NextCloud service. Audio files in NextCloud will be uploaded into a separate file for each physiotherapy department and moved to a central PainSMART-file to remove access to the audio files for all but the research team responsible for the study.

Declaration of interests

No conflicting interests. To reduce bias, the study coordinators ([name]) will not treat any patients participating in the study in their roles as physiotherapists at the participating departments in Finspång and Linköping.

Access to data

Study data will only be accessible to the PainSMART-research group and statistical support team at Linköping's University. Group level and individual patient data will be available from the research team on reasonable request following completion of the study and publication of the study results.

Dissemination

This study protocol was published via Clinicaltrials.gov to enable public access prior to the inception of patient recruitment. A full statistical analysis plan has been published on clinicaltrials.gov prior to completion of patient recruitment and start of data analysis. The study's findings will be disseminated and made publicly available in peer-reviewed publications and conference presentations. The study's results will also be disseminated through regular communication channels within healthcare and university contexts. If the

results of the study are positive the film can be hosted on the 1177 healthcare information platform and be integrated into the primary care physiotherapy MSKP care pathway in RÖ and RJL and even across Sweden.

References

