Physiotherapist consent and background data will be collected via Webropol questionnaires prior to the start of patient recruitment. English language copies of the data collection questionnaires (patient and physiotherapist PROMs and PREMs) are available from the corresponding author on request. The physiotherapists' evaluations of the initial consultation will be sent to the study coordinators via the messenger function of the electronic journal system within RÖ and RJL. All physiotherapists who have conducted at least one initial PainSMART consultation in the RCT will be sent a follow up Webropol questionnaire containing four questions. These four questions ask the physiotherapists to self-report their adherence to the study protocol for each group and rate their experiences of the participating patients' degree of preparedness for the initial consultations. For physiotherapists who consent to continue participation in the RCT for the qualitative phase, additional data will be collected via Dictaphone audio recordings of the initial physiotherapy consultation. The audio recordings will then be uploaded to Linköping University's secure NextCloud service.

Sample size

The sample size calculation for this study is based on its primary hypotheses. The calculations are based on the MCID of $2 \pm SD/4$ for the NRS for pain intensity and a minimal detectable change of $11.52 \pm SD/23.20$ for the PSEQ-10 (Dube et al., 2021; Olsen et al., 2017; Olsen et al., 2018; Ostelo et al., 2008). Sample size calculations were computed for both primary outcomes (NRS and PSEQ-10) using a Cohen's f effect size of = 0.25 (i.e. small-moderate) and a one-sided p-value of $p=0.05$ plus a statistical strength of 0.8 (=Power 80%). The largest sample size calculated was for analysis of the NRS ($n = 102$ per group) and this was adopted as the sample size for this study. To enable mediation and sub-group analyses two subgroups are required. This gives a total sample size of 408 patients. A drop-out rate of approximately 30% was factored into the randomisation sequence giving a total sample of 600 patients.

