After the first six weeks of patient recruitment (January-February 2024) an internal pilot interim analysis was performed. Of the patient participants who expressed an interest in participating in the study, 65% actually consented and completed baseline data collection. As of February 29th, 2024, response rates for the questionnaires at time points two and three were approximately 90%. To ensure sufficient follow up data for 408 patients, the number of patients to be included at baseline was revised up to 450. This revision, along with the requirement to recruit 30 to 40 additional patients for the qualitative phase, led to a new total

sample size of 490 patients. As a result of the revised sample size an additional randomisation sequence of 200 further patient participants was generated (see allocation).

Sample size for the qualitative phase

Inclusion of an additional 30 to 40 patient participants was chosen to increase the probability of achieving saturation of qualitative data and diversity of patient and physiotherapist participants with varying baseline characteristics.

[figure not shown]

Figure 4: PainSMART-RCT Directed acyclic graph (DAG) showing data collection time points and data collected at each time point. BIPQ, Brief Illness Perception Questionnaire; BPCI-2, Brief Pain Coping Inventory-2; NRS, Numerical Rating Scales; PSEQ-10, Pain Self-Efficacy Questionnaire; PROMs, patient reported outcome measures, PREMs, patient and physiotherapist reported experience measures; RCT, randomised controlled trial.

Recruitment

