This protocol outlines the principal features of the statistical analysis for this study. A full statistical analysis plan (SAP) has been published on Clinicaltrials.gov alongside this protocol and prior to the completion of patient recruitment (September 25, 2024).

Participant characteristics

Patient: Group characteristics will be presented using descriptive statistics. Baseline analysis between the intervention and control groups will be conducted to ensure the comparability of the groups.

Physiotherapist participants: Group characteristics (age, sex, department, highest educational level, number of years of clinical experience, adherence to protocol) will be presented using descriptive statistics.

Analysis of primary outcomes

Magnitude of within and between-group change on primary outcomes from baseline to 24-72 hours prior to the initial physiotherapy consultation, 24 hours post initial physiotherapy consultation and three months post-baseline will be analysed through mixed models. Data will be compared based on the 'intention to treat' (ITT) principle. Sensitivity analyses applying per-protocol, complier average causal effect (CACE) analyses and analyses applying study specific MCID associated with dichotomised anchor response on the GRoC will be explored. Sensitivity analyses to adjust for all measured baseline covariates will also be performed to investigate the presence of equipoise as the result of randomisation (Thabane et al., 2013).

Multiplicity/ type I (a) error

The outcomes collected in the study are considered as separate entities and, therefore, restrictive multiplicity penalisation of the model is not required (Dmitrienko & D'Agostino 2013). Adjustment will be used for repeated measures over time for separate test conditions.

Analysis of secondary outcomes

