- More positive and concordant patient and physiotherapist evaluations of MSKP-related shared understanding, communication, participation, involvement and emotional support at the initial physiotherapy consultation.

2. Improvements in MSKP illness perceptions and higher levels of reassurance of the benign nature of MSKP mediate improved pain intensity and pain self-efficacy as a result of exposure to the PainSMART-strategy compared to usual physiotherapy management alone.

The null hypothesis (H0) is that there is no clinically or statistically significant differences between the intervention (film) group and the control group (usual physiotherapy management).

Secondary exploratory research questions

1. What baseline factors are predictive of improved patient outcomes after exposure to the PainSMART-strategy?
2. What baseline factors are predictive of the persistence of MSKP?
3. What type of psychological factors and strategies are associated with patient outcomes after exposure to the PainSMART-strategy?
4. Is pain self-efficacy a potential mediator of the PainSMART-strategy's effect on health outcomes?
5. What are patients and physiotherapists experiences of the PainSMART-strategy?

Study Methods

Trial design

This is a two-armed, parallel group, randomised controlled trial in which the intervention group (PainSMART-strategy + usual physiotherapy management) will be compared to a control group (usual physiotherapy management). Treatment allocation is a 1:1 ratio. The control group and statistician will be blinded. One independent statistician will be blinded for the primary analyses. Another independent statistician will be responsible for database development and linkage of patient and physiotherapist data. The PainSMART-strategy is described in full in the trial protocol.

Randomisation

A computerised randomisation sequence for 800 patients into group A (Intervention group) or B (Control group) has been generated by a blinded statistician using SPSS prior to the start of patient recruitment. Participating patients will be allocated to intervention or control group based on the order of their inception to the study. The randomisation is described in full in the trial protocol.

Framework

The trial's hypotheses apply a superiority testing framework where the PainSMART-strategy is hypothesized to be superior in outcome compared to control.

Determination of Sample size

The sample size calculation is described in full in the trial protocol.

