Physiotherapists' self-reported adherence to the study protocol will be measured using one question asking whether they adhered to the protocol by posing the structured PainSMART-questions to participating patients they met from the intervention group. Similarly, one question asking whether the physiotherapist adhered to the protocol by posing the structured question to patients in the control group will also be collected to evaluate adherence. The questions regarding adherence are answered anonymously. In the second, qualitative phase of the trial, self-reported adherence will be validated against data on adherence collected through audio recorded initial physiotherapy consultations. An independent statistician will analyse the concordance between the self-rated adherence and the objective data on adherence from consultations.

- Time Frame: collected eight months post-trial start and after all participating patients in the first part of the PainSMART-trial have had their initial physiotherapy consultation. Data on physiotherapists' adherence to protocol in the qualitative phase of the trial will be collected after all participating patients have had their initial physiotherapy consultation.
- Calculation to derive outcome:

- Adherence to study protocol will be presented descriptively in the CONSORT flow chart.

Statistical Principles

Confidence intervals and P values

For one-sided tests, the nominal level of type 1 error (α) will be 0,05 and the confidence level for two-sided confidence intervals (CI) will be 95%. The outcomes collected in the study are considered as separate entities and, therefore, restrictive multiplicity penalization of the model is not required (Dmitrienko & D'Agostino 2013). Adjustment will be made for analyses with repeated measures over time for separate test conditions using Bonferroni correction. In the case that distributional assumptions do not hold, e.g., normality etc, data transformation or non-parametric statistical alternatives will be explored.

Timing and Objectives of Interim and Final Analyses

Interim monitoring and analyses

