An internal pilot interim analysis was planned and conducted after 50% of the sample had reported outcomes at time point 2 (pre physiotherapy consultation) and 3 (primary time point one, post initial physiotherapy consultation). This to evaluate the viability of the a-priori sample size calculation and the recruitment frequency. The analysis utilised linear mixed models to investigate between group difference (effect size) for change from baseline to time points 2 and 3 in outcome. The significance level for the interim analysis was $p=0.05$. After interim sample size calculation, the sample size was slightly adjusted when taking loss to follow-up into account. The sample size calculation is described in the trial protocol. The trial would have been stopped if the internal pilot interim analysis could not be performed due to not attaining 50% of the sample size at Time point 2 and 3 within 6 months. No further interim analyses are planned.

Final analysis

The trial is planned to finish recruitment of new patient participants in Dec 2024 – Jan 2025. The final three-month follow-up data collection will therefore be in Mar - Apr 2025. All outcomes will be analysed collectively.

Analysis methods

Primary outcome analysis

-Pain intensity and Pain self-efficacy

Hypothesis testing for the two primary outcomes *pain intensity* and *pain self-efficacy* (score on average pain NRS in the last 24 hours and PSEQ-10) will be based on analysis of group mean change from baseline. Baseline scores and group mean change in primary outcome scores from baseline to primary time points one and two for the intervention and control groups and the between-group change for these time points will be presented as means and CI. The within and between-group change on primary outcomes from baseline to 24 hours post initial physiotherapy consultation and three months post-baseline will be analysed according to ITT principles using a maximum likelihood approach for mixed models adjusted for a relevant covariance structure. The models will be adjusted for baseline covariates where relevant. Baseline factors that will be analysed for potential covariate adjustment include: age, sex, educational level, employment, pain duration, number of pain sites, comorbidities, days to initial physiotherapy consultation, previous healthcare interventions, ÖMPSQ risk category, self-reported sick leave and analgesic medication consumption.

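### The protocol's sample-size inputs require 51 patients per group (102 in total), not 102 per group, so the stated 80% power does not describe the trial

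*Protocol*

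**What the plan says.** The protocol's Sample size section takes an NRS difference of 2 with SD 4 and a PSEQ-10 difference of 11.52 with SD 23.20. It expresses the effect as Cohen's f = 0.25 and sets "a one-sided p-value of $p=0.05$ plus a statistical strength of 0.8". Allocation is 1:1 (Trial design). The result is given as: "The largest sample size calculated was for analysis of the NRS ($n = 102$ per group) and this was adopted".

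The next step is "To enable mediation and sub-group analyses two subgroups are required. This gives a total sample size of 408 patients". An allowance of about 30% for drop-out then leads to a randomisation sequence of 600. After the internal pilot, 408 remained the target: "To ensure sufficient follow up data for 408 patients, the number of patients to be included at baseline was revised up to 450".

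The SAP has no derivation of its own. Under Determination of Sample size it says: "The sample size calculation is described in full in the trial protocol".

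**The concern.** For two equal groups, d = 2f, so f = 0.25 is d = 0.5. At one-sided 0.05 and 80% power, an effect of that size needs about 50 patients per group, half the stated number. The later arithmetic, 102 × 2 × 2 = 408, shows that 102 really was used as a per-group figure, so this is not just a slip in labelling.

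This section is where the sample size is tied to the primary hypotheses. A reader will conclude that 102 per group gives 80% power for 2 NRS points. If that is wrong, the reader cannot tell how small a difference the trial can detect. This matters because the protocol cites 2 points as the clinically important NRS difference: a statistically significant result in a much more sensitive trial need not be near 2 points.

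**Working it through.** **Inputs**

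| Input | Value | Source |
|---|---|---|
| NRS difference, SD | 2, 4 | Protocol, Sample size |
| PSEQ-10 difference, SD | 11.52, 23.20 | Protocol, Sample size |
| Cohen's f | 0.25 | Protocol, Sample size |
| Alpha, power | one-sided 0.05, 0.80 | Protocol, Sample size |
| Allocation | 1:1 | Protocol, Trial design |

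The protocol writes the SDs after a slash. Reading them as SD = 4 and SD = 23.20 is supported by its own f: 2/4 = 0.5, so f = 0.5/2 = 0.25 exactly; and 11.52/23.20 = 0.4966, so f = 0.248.

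**Step 1. Attempt to reproduce 102 per group**

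Normal approximation: n per group = 2(z₀.₉₅ + z₀.₈₀)²/d² = 2 × 2.4865²/0.5² = 49.5, so 50.

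Exact two-sample t-test (noncentral t, df = 2n − 2, noncentrality d√(n/2)):

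| Outcome | d | n before rounding | n per group | Power at that n |
|---|---|---|---|---|
| NRS | 0.5000 | 50.15 | 51 | 0.806 |
| PSEQ-10 | 0.4966 | 50.84 | 51 | 0.801 |

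For the NRS, 50 per group gives 0.799, just short of the target. As a cross-check, the two-group F test with f = 0.25 and alpha 0.10 (equivalent to one-sided 0.05) has power 0.799 at a total of 100 and 0.806 at a total of 102. So 102 is the two-group total.

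**Step 2. Could anything else in the documents give 102 per group?**

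- Drop-out and the subgroup doubling are both applied after the 102.
- The SAP's Statistical Principles section says: "Adjustment will be made for analyses with repeated measures over time for separate test conditions using Bonferroni correction". The SAP's primary analysis has two follow-ups: "The within and between-group change on primary outcomes from baseline to 24 hours post initial physiotherapy consultation and three months post-baseline will be analysed". The protocol's version adds an earlier one: "Magnitude of within and between-group change on primary outcomes from baseline to 24-72 hours prior to the initial physiotherapy consultation". Splitting 0.05 over two comparisons (one-sided 0.025) needs 64 per group for the NRS. Splitting it over three (0.0167) needs 72.
- A two-sided 0.05 test needs 64. Power of 90% at one-sided 0.05 needs 70.
- For 102 per group to be the 80% requirement, d would have to be 0.3493, so the SD for a 2-point difference would be 2/0.3493 = 5.7, not 4.

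**Step 3. Power for 2 NRS points, SD 4**

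| n per group | one-sided 0.05 | 0.025 (two comparisons) | 0.0167 (three) |
|---|---|---|---|
| 51 | 80.6% | – | – |
| 102 | 97.2% | 94.5% | 92.3% |
| 204 | 99.97% | 99.9% | 99.8% |

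**Step 4. Difference detectable with 80% power at 204 per arm (408 in total)**

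| One-sided alpha | d | NRS (d × 4) | PSEQ-10 (d × 23.20) |
|---|---|---|---|
| 0.05 | 0.2466 | 0.99 | 5.7 |
| 0.025 | 0.2781 | 1.11 | 6.5 |
| 0.0167 | 0.2949 | 1.18 | 6.8 |

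**Step 5. The protocol's own chain with 51**

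51 × 2 groups × 2 subgroups = 204 in total, against the adopted 408.

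**The case against.** The arithmetic is hard to dispute. The stronger objections concern what follows from it.

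*The larger number may be needed.* The doubling was meant to serve mediation and subgroup analyses, and the SAP plans a moderator analysis on two ÖMPSQ risk groups. Assume an even split (the documents give none), SD 4, one-sided 0.05 and a 2-point difference between the subgroup effects. The interaction estimate then has standard error 4√(4/m) with m patients per cell. That gives about 81% power with m = 102 (408 in total) and about 55% with m = 51 (204 in total). So 408 may suit that analysis and 204 may not. This stands as a reason to keep 408. It does not rescue the 102, which the protocol attributes to the NRS calculation before it mentions subgroups.

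*The 80% is claimed for 102 per group, not for 408.* That is fair. The direct contrast is 97% against 80%; the figure at 204 describes the size actually adopted.

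*The NRS was said to give the largest requirement.* On these inputs it does not: PSEQ-10 needs slightly more before rounding (50.84 against 50.15). The authors may have used inputs or a procedure they did not report, which makes the total-read-as-per-group explanation less certain. It is also a further sign that the section does not reproduce.

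*The internal pilot checked the calculation.* Both documents say it did, but neither reports revised effect or SD inputs, and 408 was retained.

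*The error is harmless because it is conservative.* It does not harm the primary comparison. It still leaves a wrong power statement in place.

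**Conclusion.** The concern holds. On the protocol's stated inputs the requirement is 51 per group for each primary outcome, 102 in total, so the stated 102 per group is twice what the calculation gives. Power for 2 NRS points is about 97% at 102 per group and 99.97% at the adopted 204. At one-sided 0.05 and 80% power, the adopted size detects about 0.99 NRS points, roughly half the 2 points used for planning.

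These results rest on the protocol's SDs of 4 and 23.20. The protocol does not say whether they are SDs of raw scores or of change scores. No gain from covariate adjustment is credited. The detectable differences scale in proportion to the SDs. Why the figure doubled is an inference.

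This should be corrected, but it does not threaten the trial: the error makes the study larger than the stated calculation needs.

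**What to change.** Enter a dated correction in the protocol's Sample size section, for example:

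> A difference of 2 NRS points (SD 4, f = 0.25) at one-sided 0.05 and 80% power requires 51 patients per group (102 in total). The PSEQ-10 (11.52, SD 23.20) also requires 51 per group. The same doubling for two subgroups would give 204 in total. The adopted 408 exceeds this calculated requirement and is kept. With SDs of 4 and 23.20 and no credit for covariate adjustment, 204 per arm detects about 0.99 NRS and 5.7 PSEQ-10 points with 80% power at one-sided 0.05. These differences scale in proportion to the SDs.

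If the SAP's Bonferroni correction is applied to the primary follow-up comparisons, give the figures at the alpha actually used: 1.11 and 6.5 for the SAP's two follow-ups, or 1.18 and 6.8 for the protocol's three. The 204 in this text only applies the protocol's doubling rule; it is not a claim about power for a treatment-by-subgroup interaction. If the original calculation can be recovered and used other inputs, the correction should state them.

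The cost is wording in one section. No further enrolment is needed, and data collection and analysis are unchanged.
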